2.6 Exploratory/Ancillary Correlative Studies

2.6.1 Assessment of PD-L1 expression at Baseline and Post-treatment -- Immunohistochemistry (IHC) – Exploratory Laboratory Correlative Study #1

PD-L1 has been identified as an important correlative biomarker for clinical response to anti-PD-L1 and anti-PD-1 therapies. In particular, given that the function of atezolizumab is to block binding of PD-1 to PD-L1, expression of PD-L1 will be quantitated by IHC in baseline formalin-fixed paraffin-embedded tumor specimens, and from biopsies obtained after treatment. This is an important part of the correlative studies to explore whether this marker which correlates with response in other circumstances also correlates with response in this protocol population. For baseline samples, formalin-fixed, paraffin-embedded tissue block(s) from tumor obtained before treatment will be obtained by the clinical site either from archival samples obtained from the relevant pathology laboratories where they were processed and stored, or from baseline biopsy as part of this

protocol (core, punch, or excisional). Post-treatment, formalin-fixed paraffin-embedded tumor specimens will be obtained from biopsy at week 11 (core, punch, or excisional) as part of this protocol.

PD-L1 expression will be tested by IHC at HistoGeneX (Naperville, IL) with the PD-L1 SP142 clone assay, or at other agreed upon vendor.

Hypothesis: PD-L1 expression at baseline will correlate with clinical responses to atezolizumab and atezolizumab in combination with CYT107. In addition, atezolizumab administration may alter PD-L1 expression to an unknown extent.

2.6.2 Evaluation of the effect of atezolizumab with and without CYT107 on circulating Lymphocyte and Monocyte numbers and Phenotype – Exploratory Laboratory Correlative Study #2

We will assess the effects of the atezolizumab with and without CYT107 on the frequency and phenotypic character of PBMC subsets including dendritic cells (DCs), monocyte populations, T cells, NK cells, and B cells. The effect on these immune cell subtypes of checkpoint inhibitors, and other immune modulators is being investigated in other CITN trials and may provide important correlative information on the success or failure of combination immunotherapy.

A 14-color whole blood immunophenotyping assay will quantify in one panel the absolute number and proportion of T cells (both CD8+ and CD4+), NK cells (CD56+CD3-), NKT cells (CD56+CD3+), B cells (CD19+/CD20+), monocytes (CD16+), neutrophils (CD15+), as well as both myeloid DCs (CD45+HLA-DR+CD11c+CD123-) and plasmacytoid DCs (CD45+HLA-DR+CD11c-CD123+). In addition, myeloid-derived suppressor cells (MDSC) will be measured using antibodies to HLA-DR, CD11b, and CD33 in this same multiparameter flow cytometric assay. Multiparameter flow cytometry on whole blood with a 12-color panel may also be used in parallel to further define the phenotype of T cells and to identify activated T cells, T-cell subsets (including regulatory T cells). This validated panel includes the markers CD45, CD3, CD4, CD8, CD45RA, CD197 (CCR7), CD28, CD127, CD25, HLA-DR, CD279 (PD-1), CD278.

Assays will be performed under the direction of Dr. [REDACTED] in the CIML at the Fred Hutch.

Hypothesis: The combination of atezolizumab with CYT107 will perturb circulating lymphocyte and monocyte numbers and phenotypes to a yet unknown extent.

2.6.3 Multiplex Cytokines -- Multiplex ELISA – Exploratory Laboratory Correlative Study #3

Perturbations in cytokines, chemokines, and growth factors have been associated with cancers and changes in plasma cytokine concentrations of proinflammatory and immunosuppressive cytokines may correlate with clinical responses to therapy. Measureable changes in serum and plasma cytokines have been associated with checkpoint blockade therapies. Comparison of baseline plasma cytokines, chemokines

and growth factors to longitudinal measurements during therapy may improve our understanding of the immunologic effects of the combination of atezolizumab plus CYT107 on cancer. Furthermore, these assays will be used to explore whether reactive changes in cytokine levels correlates with toxicity and/or efficacy of atezolizumab and CYT107. Longitudinally collected plasma samples will be evaluated using commercial multiplex immunoassays that are quantified by immunochemiluminescence detection or other appropriate technology.

Assays will be performed at the Fred Hutch Shared Resources, or at other agreed upon vendor.

Hypothesis: The combination of atezolizumab with CYT107 will perturb cytokines, chemokines, and growth factors to a yet unknown extent.

2.6.4 Kynurenine and tryptophan (Kyn/Trp) ratios and plasma Arginine levels – Exploratory Laboratory Correlative Study #4

Over expression of indoleamine 2,3-dioxygenase (IDO) is known to result in increases in the Kyn/Trp ratio in blood and within some tumor microenvironments. Increases in Kyn/Trp ratios result in the subsequent suppression of T-cell responses and is a major mechanism of immune control. IDO is expressed by some tumors, but probably more importantly, it is expressed by lymphocytes as a normal mechanism and important mechanism to dampen immune responses. Expression of IDO (with subsequent increased Kyn/Trp ratio) may be one likely mechanism of checkpoint blockade and other immunotherapy failures. Thus, we will measure Kyn/Trp ratios in plasma taken at baseline, during treatment, and at end of treatment in this protocol to analyze, in patients who have failed clinical response to Atezolizumab plus IL-7 treatment, failure may be associated with increased Kyn/Trp levels.

In addition, another important mechanism of immune control and suppression is through the changing concentrations of arginine insofar as decreased levels of arginine in plasma (ie arginine depletion) is associated with decreases in CD4 and CD8 T-cell proliferation and Th1 functions. Arginine depletion can occur by the release by MDSCs of arginase which converts L-arginine to ornithine. This may be another mechanism of tumor evasion as myeloid suppressor cells with high arginase activity are found in tumors. Thus, we will also measure arginine levels in the same plasma samples taken at baseline, during treatment, and at end of treatment in this protocol to analyze, in patients who have failed clinical response to Atezolizumab plus IL-7 treatment, whether failure may be associated with increased arginine levels in plasma.

All assays will be performed at an agreed upon collaborator or vendor to be determined. .

Hypothesis: Failure to respond to atezolizumab plus CYT107 treatment may be associated with increased Kyn/Trp ratios and/or increased plasma arginine levels in some patients.

2.6.5 Microbiome Analyses – Exploratory Laboratory Correlative Study #5

Recent reports in preclinical mouse tumor models suggest that the gut microbiome has an effect on response to checkpoint blockade immunotherapy, and there is growing evidence that the intestinal microbiome may have major influences on antitumor immune responses. The microbiota has long been known to have profound effects on innate and adaptive immunity. However, the impact and importance of the gut microbiome in human cancer patients' responses to immunotherapy has not yet been well-characterized and will be important to determine. To begin to understand the role of the microbiome in responses to immunotherapy in this protocol, we will collect microbiome samples from patients at baseline and perform taxonomic profiling via 16 S rRNA gene sequencing and metagenomic whole-genome shotgun (WGS) sequencing. Fecal samples will be collected and stored using standard, at home stool-collection procedures, and we will assess the landscape of the gut microbiome. Sequencing data will be analyzed and compared to clinical responses to determine whether response or nonresponse to atezolizumab plus CYT107 can be correlated with specific microbiota.

Assays will be performed in collaboration with Dr. [REDACTED] at Fred Hutch or other agreed upon collaborator.

Hypothesis: The gut microbiome profile will affect the clinical response to the combination of atezolizumab with CYT107 to a yet unknown extent.

2.7 Special Studies

2.7.1 Assessment of Immunogenicity and Pharmacokinetics

The known and predicted activities of these two immunotherapeutic agents in enhancing immune responses may, in combination, influence pharmacokinetics and immunogenicity. In particular CYT107 is pharmacologically targeting lymphocytes and subject to a PK target mediated clearance (like many other blood growth factors). This is the case for G-CSF and other factors. We have validated methods to measure CYT107 blood samples for PK analysis as well as to detect and measure the presence of binding and neutralizing antibodies. We will thus measure CYT107 blood levels before the first and fourth administrations of CYT107, and at specified intervals after administration of CYT107. This would enable detection of any potential significant interference of the concomitant immunotherapies on CYT107 PK. Similarly, we will measure anti-CYT107 binding antibodies before any CYT107 administration and after the last CYT107 administration. Any subject presenting with binding antibodies will be further tested for the presence of anti-CYT107 neutralizing antibodies. While the number of patients will be too small to draw definitive conclusions, this might lead to a potential interference in the combination therapy deserving a further exploration.

3. PATIENT SELECTION

3.1 Eligibility Criteria

3.1.1 Patients must have histologically or cytologically documented locally advanced/inoperable or metastatic UBC, including renal pelvis, ureters, urinary bladder, and urethra.

Note: Mixed histology tumors allowed if predominant histology is urothelial carcinoma.

Note: Small cell or neuroendocrine carcinoma is not allowed if predominant.

3.1.2 Patients must have recurrent disease after any prior platinum-based chemotherapy regimen.

3.1.3 Patients must have measurable disease per RECIST 1.1 assessed by computed tomography (CT) scan or MRI. See [Section 11](#) for the evaluation of measurable disease.

3.1.4 Patients must be ≥ 18 years of age on day of signing informed consent document.

Because no dosing or adverse event data are currently available on the use of atezolizumab in combination with CYT107 in patients <18 years of age, children are excluded from this study, but will be eligible for future pediatric trials.

3.1.5 ECOG performance status ≤ 2 (Karnofsky $\geq 60\%$, see [Appendix A](#))

3.1.6 Patients must have a life expectancy of greater or equal to 12 weeks

3.1.7 Patients must have normal organ and marrow function as defined below:

– leukocytes	$\geq 2,500/\text{mcL}$
– absolute neutrophil count	$\geq 1,000/\text{mcL}$
– platelets	$\geq 100,000/\text{mcL}$
– hemoglobin	$\geq 8 \text{ g/dL}$
– total bilirubin	$\leq 1.5 \times$ institutional upper limit of normal (ULN) (however, patients with known Gilbert's disease who have serum bilirubin level $\leq 3 \times$ ULN may be enrolled)
– AST(SGOT)/ALT(SGPT)	$\leq 3 \times$ ULN (AST and/or ALT $\leq 5 \times$ ULN for patients with liver involvement)
– alkaline phosphatase	$\leq 2.5 \times$ ULN ($\leq 5 \times$ ULN for patients with documented liver involvement or bone metastases)
– creatinine clearance	$\geq 30 \text{ mL/min}/1.73 \text{ m}^2$ by Cockcroft-Gault: $\frac{(140 - \text{age}) \times (\text{weight in kg}) \times (0.85 \text{ if female})}{72 \times (\text{serum creatinine in mg/dL})}$

At the discretion of the treating physician, a 24-hour urine creatinine clearance could be obtained and utilized as the gold standard if creatinine clearance by Cockcroft-Gault is <30, and prevents patient enrollment on the trial.

- INR and aPTT $\leq 1.5 \times \text{ULN}$ (This applies only to patients who do not receive therapeutic anticoagulation; patients receiving therapeutic anticoagulation, such as low-molecular-weight heparin or warfarin, should be on a stable dose.)

3.1.8 Patients must provide tissue from an archival tumor sample (obtained within 2 years from screening visit) or newly obtained core, punch, or excisional biopsy of a tumor lesion if deemed relatively safe and technically feasible.

3.1.9 Female patients of childbearing potential must have a negative urine or serum pregnancy test within 72 hours before receiving the first dose of study agent(s). If the urine test is positive or cannot be confirmed as negative, a serum pregnancy test will be required.

Administration of atezolizumab may have an adverse effect on pregnancy and poses a risk to the human fetus, including embryo-lethality. CYT107 has not been tested for reproductive toxicity yet and may expose to the same risk. Women of child-bearing potential and men must agree to use adequate contraception (hormonal or barrier method of birth control; abstinence) before study entry, for the duration of study participation, and for 5 months (150 days) after the last dose of study agent. Should a woman become pregnant or suspect she is pregnant while she or her partner is participating in this study, she should inform her treating physician immediately.

3.1.10 Patients must have the ability to understand and the willingness to sign a written informed consent document.

3.1.11 Patients positive for HIV are allowed on study, but HIV-positive patients must have:

- a. A stable regimen of HAART
- b. No requirement for concurrent antibiotics or antifungal agents for the prevention of opportunistic infections
- c. A CD4 count above 250 cells/mcL and an undetectable HIV viral load on standard PCR-based tests

3.2 Exclusion Criteria

- 3.2.1 Patients with prior allogeneic bone marrow transplantation or prior solid organ transplantation.
- 3.2.2 Patients who have had chemotherapy or radiotherapy within 2 weeks (4 weeks for nitrosoureas or systemic mitomycin C) before the initiation of study treatment.
- 3.2.3 Patients who have received more than 2 systemic cytotoxic chemotherapy regimens for metastatic urothelial carcinoma.

Note: Prior perioperative chemotherapy is allowed and is not counted as a line of therapy if patient relapsed ≥ 12 months later and received additional platinum-based chemotherapy for metastatic disease.

- 3.2.4 Patients who have not recovered from adverse events (other than alopecia) due to agents administered more than 4 weeks earlier (*i.e.*, have residual toxicities $>$ Grade 1). However, the following therapies are allowed:
 - Hormone-replacement therapy or oral contraceptives
 - Herbal therapy ≥ 1 week before initiation of study treatment (herbal therapy intended as anticancer therapy must be discontinued at least 1 week before initiation of study treatment)
 - Palliative radiotherapy for bone metastases >2 weeks before initiation of study treatment
- 3.2.5 Patients who have received prior treatment with anti-PD-1, or anti-PD-L1 therapeutic antibody, or pathway-targeting agents.
 - Patients who have received prior treatment with anti-CTLA-4 may be enrolled, provided the following requirements are met:
 - Minimum of 12 weeks from the first dose of anti-CTLA-4 and >6 weeks from the last dose
 - No history of severe immune-related adverse effects from anti-CTLA-4 (NCI CTCAE Grade 3 and 4)
- 3.2.6 Patients who have received treatment with any other investigational agent within 4 weeks before initiation of study treatment.
- 3.2.7 Patients who have received treatment with systemic immunostimulatory agents (including, but not limited to, interferon [IFN]- α or interleukin [IL]-2) within 6 weeks before initiation of study treatment.
- 3.2.8 Patients who have received treatment with systemic immunosuppressive medications (including, but not limited to, oral prednisone (>10 mg/day or equivalent), cyclophosphamide, azathioprine, methotrexate, thalidomide, and antitumor necrosis factor [anti-TNF] agents) within 2 weeks before initiation of study treatment.
 - Patients who have received acute, low dose, systemic immunosuppressant

medications (e.g., a one-time dose of dexamethasone for nausea) may be enrolled.

- The use of inhaled corticosteroids, and mineralocorticoids (e.g., fludrocortisone) for patients with orthostatic hypotension or adrenocortical insufficiency is allowed.

3.2.9 Patients taking bisphosphonate therapy for symptomatic hypercalcemia.

Note: Use of bisphosphonate therapy for other reasons (e.g., bone metastasis or osteoporosis) is allowed.

3.2.10 Patients with known primary central nervous system (CNS) malignancy or symptomatic CNS metastases are excluded, with the following exceptions:

- Patients with asymptomatic untreated CNS disease may be enrolled, provided all of the following criteria are met:
 - Evaluable or measurable disease outside the CNS
 - No metastases to brain stem, midbrain, pons, medulla, cerebellum, or within 10 mm of the optic apparatus (optic nerves and chiasm)
 - No history of intracranial hemorrhage or spinal cord hemorrhage
 - No ongoing requirement for dexamethasone for CNS disease; patients on a stable dose of anticonvulsants are permitted.
 - No neurosurgical resection or brain biopsy within 28 days before initiation of study treatment
- Patients with asymptomatic treated CNS metastases may be enrolled, provided all the criteria listed above are met as well as the following:
 - Radiographic demonstration of improvement upon the completion of CNS directed therapy and no evidence of interim progression between the completion of CNS directed therapy and the screening radiographic study
 - No stereotactic radiation or whole-brain radiation within 28 days before initiation of study treatment
 - Screening CNS radiographic study ≥ 4 weeks from completion of radiotherapy and ≥ 2 weeks from discontinuation of corticosteroids

Note: Patients with CNS metastases enrolled on trial must also have a brain MRI imaging at all standard radiologic evaluation timepoints (refer to [Section 10](#))

3.2.11 Patients with known hypersensitivity to Chinese hamster ovary cell products or other recombinant human antibodies.

3.2.12 Patients who have a history of severe allergic, anaphylactic, or other hypersensitivity reactions to chimeric or humanized antibodies or fusion proteins

3.2.13 Patients with known clinically significant liver disease, including active viral, alcoholic, or other hepatitis; cirrhosis; fatty liver/NAFLD/NASH; and inherited liver disease.

- Patients with past or resolved hepatitis B infection (defined as having a negative hepatitis B surface antigen [HBsAg] test and a positive anti-HBc [antibody to

hepatitis B core antigen] antibody test) are eligible.

- Patients positive for HCV antibody are eligible only if polymerase chain reaction (PCR) is negative for HCV RNA.

3.2.14 Patients with active underlying autoimmune disease requiring systemic immunosuppressive medication (oral prednisone >10 mg/day or equivalent). Topical, inhaled, or intraarticular steroids or physiologic endocrine replacement (insulin, levothyroxine, etc.) are permitted. Patients with a history of autoimmune disease that is not currently active require consultation with the Protocol PI and/or CITN Coordinating Center.

3.2.15 Patients who have a history of idiopathic pulmonary fibrosis, pneumonitis (including drug induced), organizing pneumonia (bronchiolitis obliterans, cryptogenic organizing pneumonia, *etc.*), or evidence of active pneumonitis on screening chest CT scan. History of radiation pneumonitis in the radiation field (fibrosis is permitted).

3.2.16 Patients who have known additional malignancies other than UBC within 2 years before initiation of study treatment.

Exceptions include malignancies with a negligible risk of metastasis or death and treated with expected curative outcome (*e.g.*, non-melanomatous skin cancers), or localized prostate cancer treated with curative intent and absence of prostate-specific antigen (PSA) relapse or incidental prostate cancer.

3.2.17 Patients with active tuberculosis (TB).

3.2.18 Patients who have leptomeningeal disease.

3.2.19 Patients who have severe infections within 4 weeks before initiation of study treatment, including, but not limited to, hospitalization for complications of infection, bacteremia, or severe pneumonia.

Exception: Uncomplicated urinary tract infection will not be considered as a severe infection in these patients.

3.2.20 Patients who have signs or symptoms of infection within 2 weeks before initiation of study treatment.

3.2.21 Patients who have received oral or IV antibiotics within 2 weeks before initiation of study treatment. Patients receiving prophylactic antibiotics (*e.g.*, for prevention of a urinary tract infection or chronic obstructive pulmonary disease) are eligible.

3.2.22 Patients who have major surgical procedure, other than for diagnosis, within 28 days before initiation of study treatment or anticipation of need for a major surgical procedure

during the course of the study.

3.2.23 Patients who have had a live, attenuated vaccine within 4 weeks before initiation of study treatment or anticipation that such a live, attenuated vaccine will be required during the study and up to 5 months after the last dose of atezolizumab.

- Influenza vaccination should be given during influenza season only (approximately October to March). Patients must not receive live, attenuated influenza vaccine within 4 weeks before initiation of study treatment or at any time during the study.

3.2.24 Uncontrolled intercurrent illness including, but not limited to, symptomatic congestive heart failure (New York Heart Association Class III or IV), unstable angina pectoris, cardiac arrhythmia, recent myocardial infarction (within the last 6 months), or psychiatric illness/social situations that would limit compliance with study requirements.

3.2.25 Prisoners or subjects who are compulsorily detained (involuntarily incarcerated) for treatment of either a psychiatric or medical (*e.g.*, infectious) illness.

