5.1.4 Other procedures: Microbiome Sample Collection

Pre-treatment and post-treatment microbiome samples will be collected by patients using standard, at home stool-collection procedures using standardized fecal swab/storage devices. The samples will be stored frozen at home by patient and returned to the clinical research site at their next study visit.

Patients will be provided with fecal swab/storage devices and instructions (refer to [Appendix E](#)) at the screening visit and at the Cycle 3, Day 1 visit.

5.2 **Safety Run-in: Definition of Dose-Limiting Toxicity**

Dose-limiting toxicity is defined as any adverse event (AE) occurring within the first 28 days (*i.e.*, from Week 1 Day 1 through Week 4 Day 7), that is considered to be ***at least possibly related*** to the protocol treatment (atezolizumab, CYT107 or both), and that meets at least one of the non-hematologic or hematologic criteria below:

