10. STUDY CALENDAR

Baseline evaluations are to be conducted within 14 days before the initiation of study treatment. Scans and x-rays must be done <4 weeks (28 days) before the initiation of study treatment. In the event that the patient's condition is deteriorating, laboratory evaluations should be repeated within 48 hours before the initiation of the next cycle of therapy. Patients receiving atezolizumab will be assessed for pulmonary signs and symptoms throughout the study.

SAFETY RUN-IN/EXPERIMENTAL ARM																				
Treatment Cycle		Cycle 1				Cycle 2				Cycle 3				Subsequent Cycle (Repeat up to 2 year)			End of Tx	Post-Treatment Follow-up		
Weeks	Screening visit	Wk1 ^a	Wk2	Wk3	Wk4	Wk5	Wk6	Wk7	Wk8	Wk9	Wk10	Wk11	Wk12	Wk13	At time of D/C ± 5 days	Safety FU	Disease Assessment ^f	Survival FU		
	Within 14 days	Day 1 ± 2	Day 8 ± 2	Day 15 ± 2	Day 22 ± 2	Day 1 ± 2	Day 8 ± 2	Day 15 ± 2	Day 1 ± 2	Day 8 ± 2	Day 15 ± 2	Day 1 ± 2	Day 8 ± 2	Day 15 ± 2		30 days ± 5 post DC	Every 12 ± 1 weeks	Every 12 ± 1 weeks		
Atezolizumab		A			A			A			A									
CYT107		B	B	B	B															
Administrative procedures																				
Informed consent	X																			
Demographics	X																			
Medical history	X																			
Concurrent meds	X	X-----				-----X				-----X				X	X	X	X			
Clinical Procedures/Assessments																				
Physical exam	X	X				X			X			X			X	X				
Vital signs ^b	X	X	X	X	X	X			X			X			X	X				
Height	X																			
Weight	X	X	X	X	X	X			X			X			X	X				
Adverse event evaluation		X-----				-----X				-----X				X	X	X				
Immune-related AEs evaluation		X-----				-----X				-----X				X	X	X				
Performance status	X	X	X	X	X	X			X			X			X	X				
EKG (as indicated)	X																			
Laboratory Assessments (Safety Labs)																				
CBC w/diff, plt	X	X	X	X	X	X			X			X			X	X				
Serum chemistry ^c	X	X	X	X	X	X			X			X			X	X				
Pregnancy Test (Urine or Serum HCG)	X ^d														X					
Efficacy Measurements																				
Tumor measurements	Within 28 days	Tumor measurements are repeated every 9±1 weeks . Documentation (radiologic) must be provided for patients removed from study for progressive disease.												X		X				
Radiologic evaluation ^k	Within 28 days	Radiologic measurements should be performed every 9 ± 1 weeks .												X		X				

SAFETY RUN-IN/EXPERIMENTAL ARM																				

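### Patients last treated about 2 to 4 weeks before Day 1 can enter with unresolved toxicity that would exclude a patient treated longer ago (3.2.2 against 3.2.4)

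*Combined protocol and SAP*

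**What the plan says.** Criterion 3.2.2 excludes "Patients who have had chemotherapy or radiotherapy within 2 weeks (4 weeks for nitrosoureas or systemic mitomycin C) before the initiation of study treatment". Criterion 3.2.4 then excludes "Patients who have not recovered from adverse events (other than alopecia) due to agents administered more than 4 weeks earlier", and it defines lack of recovery as residual toxicity above Grade 1. The list of permitted therapies under 3.2.4 includes "Palliative radiotherapy for bone metastases >2 weeks before initiation of study treatment". For treated CNS metastases, 3.2.10 sets a longer interval: "No stereotactic radiation or whole-brain radiation within 28 days before initiation of study treatment".

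Separately, 3.1.7 states: "Patients must have normal organ and marrow function as defined below". The limits that follow are blood counts, liver and renal values, and coagulation. Section 10 says when they are measured: "Baseline evaluations are to be conducted within 14 days before the initiation of study treatment".

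Section 5.2 defines a DLT as "any adverse event (AE) occurring within the first 28 days" that is at least possibly related to atezolizumab, CYT107 or both and meets the listed grade criteria. Sections 5 and 13.3 let the run-in pass with no more than one DLT among six patients and suspend enrollment at two or more.

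**The concern.** A washout and a recovery requirement normally work together: the first sets how recent prior therapy may be, and the second requires that its effects have settled. Here they cover different patients. The patients closest to their prior therapy, and so most likely to carry its toxicity, are the ones with no general duty to have recovered. Every patient has had platinum chemotherapy (3.1.2), so the therapies concerned are the usual ones for this population. No reason for the difference is given.

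Entry safety is at stake first. The second issue is how clearly the run-in can be read. If toxicity present at entry worsens during the 28-day window, the question of whether study drug contributed is hard to answer. The error can go either way: carry-over counted as a DLT, or a genuine DLT put down to prior therapy.

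**Working it through.** **Step 1. Locate the gap.** 3.2.2 clears a patient once 2 × 7 = 14 days have passed. 3.2.4 applies only beyond 4 × 7 = 28 days. The uncovered interval is days 15 to 28. I read the 3.2.4 interval as counted back from the start of study treatment, as in 3.2.2; 3.2.4 does not name the date.

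**Step 2. Which therapies fall in it.**

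| Prior therapy | Washout | Days 15–28 open? |
|---|---|---|
| Most chemotherapy and radiotherapy (3.2.2) | 2 weeks | Yes |
| Palliative bone radiotherapy (3.2.4 list) | more than 2 weeks | Yes |
| Nitrosoureas, systemic mitomycin C (3.2.2) | 4 weeks | No |
| Brain radiation, treated CNS metastases (3.2.10) | 28 days | No |
| Investigational agents (3.2.6) | 4 weeks | No |

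The recovery clause fits the 4-week washouts. It does not fit the 2-week one.

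**Step 3. Do other criteria close it?** 3.1.7 covers laboratory values only, and these may be up to 14 days old at Day 1. 3.2.15 covers pneumonitis, and 3.2.19 to 3.2.21 cover infection and antibiotics. 3.2.24 covers uncontrolled intercurrent illness. ECOG status up to 2 is allowed (3.1.5). None of these generally excludes fatigue, diarrhea or neuropathy above Grade 1.

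**Step 4. Can such toxicity reach the DLT count?** Possible relation to study drug is enough. In 5.2.2 only the laboratory exception mentions baseline status, and there is no general rule on worsening from baseline. Short episodes are exempt: Grade 3 fatigue up to 7 days, and Grade 3 diarrhea up to 72 hours with adequate management. Longer episodes are not, and neuropathy has no exception. As the Section 10 tables read here, adverse event evaluation starts in week 1, not at screening.

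**Step 5. What one misclassified patient does to the run-in.** The stated limit reproduces: 1/6 = 16.7%. With true DLT rate p, the chance of suspension is 1 − (1 − p)^6 − 6p(1 − p)^5. The documents give no true rate, so p is assumed to range from 5% to 16.7%. Misclassifying one patient, in either direction, changes the decision only when exactly one of the other five has a DLT: 5p(1 − p)^4.

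| True rate p | Suspension, no misclassification | One misclassified patient is decisive |
|---|---|---|
| 5% | 1 − 0.735 − 0.232 = 3.3% | 5 × 0.05 × 0.95^4 = 20.4% |
| 10% | 1 − 0.531 − 0.354 = 11.4% | 5 × 0.10 × 0.90^4 = 32.8% |
| 16.7% | 1 − 0.335 − 0.402 = 26.3% | 5 × (1/6) × (5/6)^4 = 40.2% |

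The last column is conditional on a misclassification having happened. How often that would be is not in the documents, so no overall change in the pass probability follows.

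**The case against.** The strongest reply is that the gap is narrow and already guarded. The 4-week and 28-day windows close it for several therapies, and the laboratory, lung and infection criteria remove much of what recent chemotherapy causes. Toxicity attributed to prior therapy is not a DLT, 5.2.2 exempts short episodes of the commonest complaints, and a Toxicity Evaluation Committee assesses the events. The recovery rule is also a clinical choice. Most of this stands and limits the consequence. It does not remove the mismatch, because no general criterion covers non-laboratory, non-infectious toxicity from chemotherapy or radiotherapy given 2 to 4 weeks earlier.

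A reader might infer more than the documents support:

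- *That one carry-over event stops the trial.* It does not: one DLT passes and two suspend enrollment.
- *That the DLT count will be contaminated.* This would need carry-over to worsen, to outlast any exception, and to be misjudged by the committee. It is possible in ambiguous cases but does not follow from the criteria.
- *That the loss in pass probability can be stated.* That needs the share of patients in the gap and their excess risk of a counted event. Neither is given, and attribution error could also run the other way.
- *That the efficacy comparison suffers.* The run-in patients are analyzed separately (13.2), both randomized arms share the same eligibility criteria, and the 48-patient calculation does not depend on them.

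**Conclusion.** The point holds as an inconsistency between two eligibility criteria. Read literally, 3.2.2 and 3.2.4 admit a patient last treated about 15 to 28 days before Day 1 with non-laboratory toxicity above Grade 1, and exclude the same patient if the causative agent was given earlier. The main consequence is for safety at entry. The second is harder DLT attribution in a six-patient run-in, where one misclassified patient would be decisive 20% to 40% of the time over the assumed DLT rates. Committee review and the 5.2.2 exceptions reduce the chance of such a misclassification by an amount the documents do not allow one to estimate. The conclusion rests on the literal wording and on counting both intervals from the start of treatment. The point is worth correcting because the change is small, not because a large effect has been shown.

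**What to change.** Reconcile 3.2.2 and 3.2.4 so that the recovery requirement and the washout cover the same patients, and name the date from which the 3.2.4 interval is counted. The toxicity grade and the interval are the sponsor's clinical decision; this point does not choose them. If the difference is intended, the protocol should give the reason and say in Section 5.2 how toxicity already present at entry is handled in DLT assessment.

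The change is about one phrase in the eligibility criteria. If it widens the recovery requirement, a few patients will wait for recovery before entry. Sample size and the analysis plan do not change.
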